2.1 OBJECTIVES AND SCIENTIFIC AIMS

Primary Objective:

- To determine the efficacy of the combination of durvalumab and tremelimumab in patients with I) carcinoma with a small-cell component (or neuroendocrine features) II) predominant squamous cell carcinoma or III) predominant adenocarcinoma or the urothelial tract as measured by best ORR, which will include the sum of complete response (CR) + partial response (PR) by RECIST v 1.1.

Secondary Objectives:

- To assess for other parameters of clinical outcome of the combination of durvalumab plus tremelimumab in patients with I) carcinoma with a small-cell component (or neuroendocrine features) II) predominant squamous cell carcinoma or III) predominant adenocarcinoma or the urothelial tract including:
 - Progression Free Survival (PFS) and duration of response (DOR) rate by RECIST v1.1
 - Overall survival (OS)
 - Best ORR (CR + PR), PFS, and DOR by Immune-related Response Criteria in Solid Tumors (irRECIST) criteria
 - Clinical benefit (CR + PR + Stable Disease [SD]) rate by RECIST v1.1 and irRECIST
 - Rate of immune-related Adverse Events (irAE)
 - Rate of serious adverse events (SAE)

Exploratory Objectives:

- To determine differences in the immune microenvironment between bladder cancer histologies as determined by PD-L1 staining, immune related gene expression profiles, and multiplex immunofluorescence (IF) for multiple immune cell subsets
- To determine whether bladder cancer histology and the associated immune microenvironment as defined above is predictive of the clinical benefit rate (CBR).
- To determine if T cell clonality in tumors and blood will be associated with the CBR.
- To determine whether immune suppressive cells types in the peripheral blood and in tumors will correlate with a decreased CBR.

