14.1 BIOSTATISTICS

14.2 Primary Endpoint and Sample Size Justification

The three histologic groups (Small-Cell, Squamous Cell Carcinoma, and Adenocarcinoma) will be part of the same cohort given they are expected to have similar response rates. With an unacceptable rate of 5% and acceptable rate of 20%, and setting type I error to 5% and power to 80%, with Simon's minimax two-stage design, we will enroll 13 patients in the first stage. Non-transitional cell carcinoma of the urothelial tract is a rare entity. Single, arm phase II studies have been published, but only in the front-line setting and only in small cohorts of patients (summarized in table 1). To our knowledge, there is no published data on response rates to second-line chemotherapy in patients with non-transitional cell carcinoma of the urothelial tract. The patient population under study has no standard treatment options and, in our group's clinical experience, rarely experiences a meaningful clinical benefit from chemotherapy. Therefore, we have elected to set the null hypothesis at an ORR of 5%. If no

patients in the first 13 have achieved a response, enrollment for stage 2 will be halted until the 13 subjects in the first stage have been assessed for response (window of 2 disease assessment scans following initiation of treatment). If we see 1 or more responses in any of the histologies in the first stage, we continue to the second stage where we will enroll additional 14 patients. If, at the end of the study, we see 4 or more responses out of the total of 27 patients, we will consider the therapy promising. As an exploratory analysis, we will also estimate the response rate of the small cell/neuroendocrine, predominant squamous, and predominant adenocarcinoma cohorts separately as a proportion of responders with the corresponding confidence interval, although formal comparisons between the three cohorts are not planned.

The response evaluable population is defined as all patients with a baseline disease assessment who have received at least one treatment with durvalumab and tremelimumab on study and have had either at least one post-baseline disease assessment or withdrawn from study treatment prior to post-baseline disease assessment due to clinical progression or death.

As described in section 9.2, patients may undergo retreatment after disease progression. The primary endpoint of best overall response is based on the best response from the first round of treatment.

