14.4 Exploratory analyses

Listed below are immune related hypotheses and the plan for exploratory analyses. Additional or different investigational methods will be used to characterize and measure components of the immune response based upon the latest available technology at the time of analysis. Specimens will also be stored for future studies related to non-TCC of the urothelial tract immunity for those patients who have consented to an institutional biobanking protocol (e.g. 06-107, 12-245, etc). If tissue availability or funding is limited, assay priority will be determined at the investigators discretion.

The exploratory hypotheses listed below are hypothesis generating. As such, all four of the exploratory analyses will be descriptive and graphical in nature. To test the associations between binary CBR or subtypes and biomarkers we will use Fisher's exact or Wilcoxon rank sum tests for binary or continuous variables respectively.

Immune Hypothesis 1: The tumor microenvironment will vary based on the histologic subtype of non-TCC of urothelial tract.

Proposed biomarker evaluation: Analysis of immune infiltrate will be performed using immunohistochemistry (IHC), immunofluorescence (IF), and computational approaches based upon RNA sequencing data. Immune regulatory molecules and populations of cells analyzed may include, but will not be limited to PD-L1, CD4, CD8, Tregs, B cells, macrophages, and dendritic cells and expression of biologically relevant/phenotypic markers thereof. The Ventana SP263 assay (performed in accordance with the package insert on the Ventana Benchmark platform (Ultra or XT) should be used to measure PD-L1.

Immune Hypothesis 2: The composition and phenotype of the tumor microenvironment at baseline will correlate with the clinical benefit rate (CBR).

Proposed Biomarker Evaluation: See immune hypothesis 1.

Immune Hypothesis 3: High T cell clonality in the tumor plus peripheral expansion of dominant tumor-resident T cell receptor clones will be associated with the CBR.

Proposed Biomarker Evaluation: We will perform high throughput DNA sequencing of the CDR3 region of the TCR beta chain in baseline tumors and pre- and post-treatment peripheral blood.

Immune Hypothesis 4: High levels of myeloid derived suppressor cells (MDSCs) and T regulatory cells (Tregs) in the peripheral blood and high levels of immunosuppressive tumor associated myeloid cells and T regulatory cells in will correlate with a decreased CBR.

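### Does Section 14.4 need a three-group test for continuous biomarkers compared across the three histologic subtypes?

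*Combined protocol and SAP*

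**What the plan says.** Section 14.4 (Exploratory analyses) covers all biomarker testing in one sentence. For "associations between binary CBR or subtypes and biomarkers" it names Fisher's "exact or Wilcoxon rank sum tests for binary or continuous variables respectively". Just before that it states that "all four of the exploratory analyses will be descriptive and graphical in nature" and that the hypotheses are hypothesis generating.

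The subtype comparison belongs to Immune Hypothesis 1: "The tumor microenvironment will vary based on the histologic subtype of non-TCC of urothelial tract". The matching exploratory objective in Section 2.1 is "To determine differences in the immune microenvironment between bladder cancer histologies as determined by PD-L1 staining", together with gene expression profiles and multiplex immunofluorescence. The markers are left open: they "may include, but will not be limited to PD-L1, CD4, CD8, Tregs, B cells, macrophages, and dendritic cells".

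Section 14.2 fixes the number of groups: "The three histologic groups (Small-Cell, Squamous Cell Carcinoma, and Adenocarcinoma) will be part of the same cohort". Inclusion criterion 3 in Section 6.2 places each patient in one of the three. Section 14.2 also plans separate response rates by histology, "although formal comparisons between the three cohorts are not planned". That clause concerns response, not biomarkers. A further objective in Section 2.1 asks whether histology and the immune microenvironment predict clinical benefit; it gives no contrast scheme either.

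**The concern.** A rank sum test takes two samples. Applied to a continuous marker and a three-level factor, it cannot give one overall answer to whether the marker varies by histology. The analyst must first choose: three pairwise tests, each histology against the other two combined, or one selected pair. The plan does not say which. Reading the word binary as also governing subtypes does not help, because no two-level grouping of the histologies is defined anywhere.

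If the choice is made after the data are seen, two things could go wrong. The chance that at least one comparison looks nominally significant depends on how many are run. And a reader of the eventual report might not know whether a p-value is an overall test or one of several. Although the section calls itself descriptive, it does go on to name tests, so p-values are to be expected.

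**Working it through.** **Which analyses are affected**

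| Analysis | Groups | Named test | Usable as written? |
|---|---|---|---|
| Binary marker by clinical benefit | 2 | Fisher | yes |
| Continuous marker by clinical benefit (Hypotheses 2 to 4) | 2 | rank sum | yes |
| Binary marker by subtype (Hypothesis 1) | 3 | Fisher | yes, on a 3×2 table |
| Continuous marker by subtype (Hypothesis 1) | 3 | rank sum | only after contrasts are chosen |

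Only the last row is open.

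**Inputs.** From the plan: three subtypes (Section 14.2); 27 patients in all, or 13 if none of the first 13 respond (Section 4.2). Stopping at 13 is not remote: at the 5% null response rate its probability is 0.95^13 = 0.513. Section 14.4 states no figure, so there is none to reproduce. Assumed, because the documents give neither: a two-sided 0.05 level and the split of patients over the subtypes.

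**False-positive rate per marker.** If three tests were independent, the chance of at least one p < 0.05 would be 1 − 0.95³ = 14.3%. Pairwise tests share groups, and exact p-values are discrete, so the true rate is lower. It was simulated with 40,000 data sets per split, exact rank sum p-values, no ties, and Kruskal-Wallis by chi-square on 2 df. Repeat runs agree within about half a percentage point.

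| Split | Any of 3 unadjusted pairs | Any pair below 0.05/3 | Kruskal-Wallis |
|---|---|---|---|
| 9/9/9 | 10.3% | 3.9% | 4.7% |
| 6/9/12 | 11.6% | 3.6% | 4.5% |
| 4/8/15 | 11.7% | 4.1% | 4.4% |
| 2/5/20 | 7.5% | 2.4% | 3.5% |
| 4/4/5 (stop at 13) | 8.0% | 3.0% | 4.2% |
| 3/3/7 (stop at 13) | 6.4% | 0.0% | 3.4% |
| 2/4/7 (stop at 13) | 4.3% | 1.3% | 2.9% |

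The last row can be checked by hand. The smallest two-sided p-value is 2/C(6,2) = 2/15 = 0.133 for 2 against 4, and 2/C(9,2) = 2/36 = 0.056 for 2 against 7. Neither pair can reach 0.05. Only 4 against 7 can, and its exact size is 14/C(11,4) = 14/330 = 4.2%.

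The range is therefore about 4% to 12% for unadjusted pairs and about 3% to 5% for Kruskal-Wallis.

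**Detection of a true difference.** Assume normal data and a 1-SD shift in one histology.

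| Split, shifted group | Unadjusted pairs | Adjusted pairs | Kruskal-Wallis | Unadjusted pairs minus Kruskal-Wallis |
|---|---|---|---|---|
| 9/9/9, any | 62% | 43% | 48–49% | 13–14 points |
| 6/9/12, group of 6 | 56% | 33% | 38% | 18 points |
| 6/9/12, group of 9 | 66% | 42% | 49% | 17 points |
| 6/9/12, group of 12 | 68% | 45% | 53% | 15 points |

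Over six splits totalling 20 to 27 patients the difference runs from 13 to 19 points. Part of that advantage is the price of the higher false-positive rate in the table above, so neither choice dominates.

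**The case for a change.** The best case for amending the text is that it would take one or two sentences and no new data, would leave the design untouched, and would settle the contrasts before anyone sees the biomarker results. In splits near the full 27 patients, unadjusted pairwise testing at least doubles the chance of a nominally significant null result per marker (10.3% against 4.7% at 9/9/9). Three different schemes fit the present wording.

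The facts in this stand: the wording is incomplete, and a careful author would have separated the two uses of the tests. The inference to a needed change does not. Running the named test between pairs of subtypes is ordinary practice and requires no different method. Fisher's test on a 3×2 table is accepted here without being spelled out, and the rank sum test deserves the same latitude. The doubling is against a 0.05 threshold that the plan does not set for these analyses, and it shrinks or disappears at the small or very unequal splits that the plan permits. The remaining risk, that an overall p-value is confused with a pairwise one, arises only if the report fails to name its test. With the marker list itself left open by design, fixing the contrast for each marker would add little protection.

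**Conclusion.** No change follows. This is a gap in detail that an analyst facing three groups will fill sensibly, either with labelled pairwise rank sum tests or with a Kruskal-Wallis test. It is confined to continuous markers by subtype under Immune Hypothesis 1. Nothing in the primary endpoint, the 27-patient sample size, the decision rule or the secondary endpoints depends on it. Replacing the rank sum test with Kruskal-Wallis would exchange a lower false-positive rate (about 3% to 5% against 4% to 12% per marker) for about 13 to 19 points less detection of a 1-SD shift, a doubtful gain in a hypothesis-generating screen. The false-positive rates rest on the assumed 0.05 level, the assumed splits and the absence of ties; the detection figures also assume normal data. The conclusion does not rest on them: it rests on the descriptive status that the plan gives these analyses and on the named test being valid between pairs.

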15.1 RESEARCH PARTICIPANT REGISTRATION AND RANDOMIZATION PROCEDURES

15.2 Research Participant Registration

Confirm eligibility as defined in the section entitled Inclusion/Exclusion Criteria. Obtain informed consent, by following procedures defined in section entitled Informed Consent Procedures. During the registration process registering individuals will be required to complete a protocol specific Eligibility Checklist. The individual signing the Eligibility Checklist is confirming whether or not the participant is eligible to enroll in the study. Study staff are responsible for ensuring that all institutional requirements necessary to enroll a participant to the study have been completed. See related Clinical Research Policy and Procedure #401 (Protocol Participant Registration).

15.3 Randomization

N/A

16.0 DATA MANAGEMENT ISSUES

A MSKCC Research Study Assistant (RSA) will be assigned to the study. The responsibilities of the RSA include project compliance, data collection, abstraction and entry, data reporting, regulatory monitoring, problem resolution and prioritization, and coordinate the activities of the protocol study team.

The data collected for this study will be entered into a MSKCC secure database (CRDB). Source documentation will be available to support the computerized patient record.

16.1 Quality Assurance

Weekly registration reports may be generated to monitor patient accruals and completeness of registration data. Routine data quality reports will be generated to assess missing data and inconsistencies. Accrual rates, accuracy of evaluations, and follow-up will be monitored periodically throughout the study period. Potential problems will be brought to the attention of the study team.

16.2 Data and Safety Monitoring

The Data and Safety Monitoring (DSM) Plans at Memorial Sloan-Kettering Cancer Center (MSKCC) were approved by the National Cancer Institute in September 2001. The plans address the new policies set forth by the NCI in the document entitled "Policy of the National Cancer Institute for Data and Safety Monitoring of Clinical Trials" which can be found at: <http://www.cancer.gov/clinicaltrials/conducting/dsm-guidelines/page1>. The DSM Plans at MSKCC were established and are monitored by the Office of Clinical Research. The MSKCC Data and Safety Monitoring Plans can be found on the MSKCC Intranet at: <http://inside2/clinresearch/Documents/MSKCC%20Data%20and%20Safety%20Monitoring%20Plans.pdf>

There are several different mechanisms by which clinical trials are monitored for data, safety and quality. There are institutional processes in place for quality assurance (e.g., protocol monitoring, compliance and data verification audits, therapeutic response, and staff education on clinical research QA) and departmental procedures for quality control, plus there are two institutional committees that are responsible for monitoring the activities of our clinical trials programs. The committees: *Data and Safety Monitoring Committee (DSMC)* for Phase I and II clinical trials, and the *Data and Safety Monitoring Board (DSMB)* for Phase III clinical trials report to the Center's Research Council and Institutional Review Board.

During the protocol development and review process, each protocol will be assessed for its level of risk and degree of monitoring required. Every type of protocol (e.g., NIH sponsored, in-house sponsored, industrial sponsored, NCI cooperative group, etc.) will be addressed and the monitoring procedures will be established at the time of protocol activation.

17.1 PROTECTION OF HUMAN SUBJECTS

The study will be performed in accordance with ethical principles that have their origin in the Declaration of Helsinki and are consistent with ICH/Good Clinical Practice, and applicable regulatory requirements Subject data protection.

Potential risks to human subjects include drug-related toxicity, pain and discomfort associated with durvalumab and tremelimumab, placement of IV catheters, phlebotomy, and possible psychological discomfort from the stresses associated with obtaining imaging studies (e.g., CT scan). The side effects and potential toxicities of durvalumab and tremelimumab are listed in the informed consent form. All efforts will be made to avoid any complication by completely reviewing patients' symptoms, providing appropriate management, and monitoring blood tests. If an adverse medical event occurs, the patient will first contact the primary oncologist or the principal investigator. At nights and weekends, there is an oncology physician on call at all times. Patients may either call or come directly to

the urgent care center at Memorial Hospital (or to their local emergency room) to be seen. Patients suffering serious adverse reactions must be carefully followed and all follow-up information recorded.

Alternatives/Options for treatment

Patients can elect to receive chemotherapy or supportive/hospice care. They can also elect to participate in another clinical trial. Participation in a clinical trial is voluntary.

Costs

The patient will be responsible for all costs related to treatment and complications of treatment. Durvalumab and tremelimumab will be provided without charge. Costs to the patient (or third party insurer) will include the cost of hospitalizations, routine blood tests and diagnostic studies, office visits, baseline EKG, other medications such as antibiotics and doctor's fees. Tests done solely for research purposes will not be billed to the patient.

17.2 Privacy

MSK's Privacy Office may allow the use and disclosure of protected health information pursuant to a completed and signed Research Authorization form. The use and disclosure of protected health information will be limited to the individuals described in the Research Authorization form. A Research Authorization form must be completed by the Principal Investigator and approved by the IRB and Privacy Board (IRB/PB).

17.3 Serious Adverse Event (SAE) Reporting

An adverse event is considered serious if it results in ANY of the following outcomes:

- Death
- A life-threatening adverse event
- An adverse event that results in inpatient hospitalization or prolongation of existing hospitalization
- A persistent or significant incapacity or substantial disruption of the ability to conduct normal life functions
- A congenital anomaly/birth defect
- Important Medical Events (IME) that may not result in death, be life threatening, or require hospitalization may be considered serious when, based upon medical judgment, they may jeopardize the patient or subject and may require medical or surgical intervention to prevent one of the outcomes listed in this definition

Note: Hospital admission for a planned procedure/disease treatment is not considered an SAE.

SAE reporting is required as soon as the participant signs consent. SAE reporting is required for 30-days after the participant's last investigational treatment or intervention. Any

events that occur after the 30-day period and that are at least possibly related to protocol treatment must be reported.

If an SAE requires submission to the IRB office per IRB SOP RR-408 „Reporting of Serious Adverse Events”, the SAE report must be sent to the IRB within 5 calendar days of the event. The IRB requires a Clinical Research Database (CRDB) SAE report be submitted electronically to the SAE Office as follows:

For IND/IDE trials: Reports that include a Grade 5 SAE should be sent to [contact]. All other reports should be sent to [contact].

For all other trials: Reports that include a Grade 5 SAE should be sent to [contact]. All other reports should be sent to [contact].

The report should contain the following information:

Fields populated from CRDB:

- Subject's initials
- Medical record number
- Disease/histology (if applicable)
- Protocol number and title

Data needing to be entered:

- The date the adverse event occurred
- The adverse event
- The grade of the event
- Relationship of the adverse event to the treatment (drug, device, or intervention)
- If the AE was expected
- The severity of the AE
- The intervention
- Detailed text that includes the following
 - A explanation of how the AE was handled
 - A description of the subject's condition
 - Indication if the subject remains on the study
- If an amendment will need to be made to the protocol and/or consent form
- If the SAE is an Unanticipated Problem

The PI or Co-PI's signature and the date it was signed are required on the completed report.

The CRDB SAE report should be completed as per above instructions. If appropriate, the report will be forwarded to the FDA by the SAE staff through the IND Office.

17.3.1 Requirement SAE Reporting to AstraZeneca/MedImmune

17.2.1.1 Serious adverse events

* **Send deidentified SAE report and accompanying cover page by way of email to AstraZeneca's designated mailbox:**
[contact]

If a non-serious AE becomes serious, this and other relevant follow-up information must also be provided to AstraZeneca and the FDA.

The study PI will request additional information for any subject with ongoing AE(s) / SAE(s) at the end of the study, if judged necessary

Serious adverse events that do not require expedited reporting to the FDA still need to be reported to AstraZeneca preferably using the MedDRA coding language for serious adverse events. This information should be reported on a monthly basis and under no circumstance less frequently than quarterly.

AstraZeneca/MedImmune retains the right to request additional information for any subject with ongoing AE(s)/SAE(s) at the end of the study, if judged necessary.

